#### **3.2.5.2. Injection site reactions will include the signs and symptoms reported along with the AE of injection site reaction. Laboratory Results**

To determine if there are any clinically significant laboratory abnormalities, the safety laboratory tests will be assessed against the criteria specified in the sponsor reporting standards. The assessment will take into account whether each participant's baseline test result is within or outside the laboratory reference range for the particular laboratory parameter.

Change from baseline will be calculated for each of the lipid panel endpoints (total cholesterol, HDL-cholesterol, non-HDL-cholesterol, calculated LDL cholesterol and triglycerides) at the Week 22 timepoint.

### 3.2.5.3. Vital Signs

The change from baseline for vital signs (supine systolic and diastolic blood pressure and pulse rate) will be calculated for all post baseline timepoints.

The maximum increase/decrease from baseline over all measurements taken post-dose will be calculated for supine systolic and diastolic blood pressures and pulse rate. The maximum increase from baseline will be calculated as the maximum change from baseline for a participant, except in the case where a participant does not show an increase. In such an instance, the minimum decrease should be taken. Similarly, the maximum decrease from baseline will be determined by selecting the minimum value of the changes from baseline. In cases where a participant does not show a decrease, the minimum increase should be taken.

## 3.3. Other Endpoint(s)

### 3.3.1. Change from baseline in KCCQ-23 CSS, OSS, TSS, and physical limitation at Week 22 (Cohorts A and D combined)

See Section 3.2.1.

### 3.3.2. Responses as defined by a $\geq 5$ -point increase from baseline in KCCQ-23 CSS, OSS, TSS, and physical limitation at Week 22 (Cohorts A and D combined)

See Section 3.2.2.

### 3.3.3. Change from baseline in 6MWD at Week 22 (Cohorts A and D combined)

See Section 3.2.3.

### 3.3.4. Change from baseline in PROMIS Fatigue 7a at Week 22 (Cohorts A and D combined)

See Section 3.2.4.

### 3.3.5. Response as defined by a $\geq 10$ -point and $\geq 15$ -point increase in KCCQ-23 CSS, OSS, TSS, and physical limitation at Week 22 (Cohorts A, C and D)

See Section 3.1.1.

Each of these endpoints will have two levels: 'Response' and 'Non-response'. The former will be based on participants having a  $\geq 10$ -point or 15-point increase from baseline in KCCQ-23 CSS, OSS, TSS, or physical limitation, respectively. Otherwise, participants will be classed as having a 'Non-response'. Participants with an intercurrent event of premature discontinuation of IP prior to Week 22 will have their Week 22 value censored (if not missing). Missing or censored values at Week 22 will be imputed as described in Section 5.3. Note that data for participants who die during the study will be included in the imputation but will then be classed as having a 'Non-response' after imputation.

These endpoints will be calculated for all post-baseline timepoints.

### **3.3.6. Absolute and change from baseline in PGI-S at Week 22 and PGI-C at Week 22 (Cohorts A, C and D)**

#### **3.3.6.1. PGI-S**

*The PGI-S is a measure consisting of 4 questions that ask the study participants to evaluate the severity of their fatigue, shortness of breath, overall symptoms of HF, and daily activity limitations over the past 14 days on a 5-point verbal response scale that ranges from “None” to “Very severe”.*

*The PGI-S is recommended by the FDA for use as an anchor measure to generate an appropriate threshold that represents meaningful within-individual change in the target patient population.*

The change from baseline in PGI-S will be calculated for all post-baseline timepoints.

#### **3.3.6.2. PGI-C**

*The PGI-C is a measure consisting of 4 questions that ask study participants to rate the overall change in their fatigue, shortness of breath, overall symptoms of HF, and ability to do daily activities on a 5-point verbal rating scale ranging from “Much better” to “Much worse”.*

*The PGI-C is recommended by FDA for use as an anchor measure to generate an appropriate threshold that represents meaningful within-individual change in the target patient population.*

### **3.3.7. Change from baseline in body weight at Week 22 (Cohorts A, C and D)**

*Weight will be recorded using a calibrated scale (with the same scale used if possible for the duration of the study) reporting weight in either lb or kg, and accuracy to the nearest 0.2 lb. (or 0.1 kg).*

Absolute change from baseline in body weight will be calculated for all post-baseline timepoints.

### **3.3.8. Change from baseline in daily activity measures based on accelerometry at Week 22 (Cohorts A, C and D)**

*An activity monitor should be placed on the participant’s non-dominant wrist from SV2 to Day 1 and from Week 20 to Week 22. The participant should be asked to wear the activity monitor continuously during these periods.*

The following daily endpoints will be provided from the activity monitor:

- \*Moderate to Vigorous Physical Activity Time (MVPA; mins/day)
- \*Total vector magnitude (counts/1000/day)
- \*Non-sedentary Physical Activity (mins/day)

- \*Number of Steps per Day (steps/day)
- \*Max 6 mins of activity level (M6mins; counts/day)
- Sedentary Activity Time (mins/day)
- Light Activity Time (mins/day)
- Moderate Activity Time (mins/day)
- Vigorous Activity Time (mins/day)
- Max 15/60 mins of activity level (M15mins, M60mins; counts/day)
- Average activity counts for the most active 10 hours of the day (M10hr; counts/day)
- Average activity counts for the least active 5 hours of the day (L5hr; counts/day)
- Total Activity Count for Axis X (counts/1000/day)
- Total Activity Count for Axis Y (counts/1000/day)
- Total Activity Count for Axis Z (counts/1000/day)
- Wear Time (mins/day)
- Wear Awake Time (mins/day)

Note: \* Priority endpoints

Fortnightly averages (on Day 1 and at Week 22) will be calculated as the mean taken over the 14 days immediately prior (e.g. if the Week 22 visit occurs on Day 155, the Week 22 average will be taken over Days 141 to 154). These fortnightly averages will not overlap a dosing visit, i.e. if the Week 20 visit occurs on Day 143, the Week 22 average will only be taken over Days 143 to 154. If fewer than 4 compliant days of scores are recorded, the mean should be treated as missing (a day is defined as compliant if at least 10 hours of awake wear and/or 18 hours of total wear time are present).

Baseline is defined as the mean taken over the 14 days prior to Day 1 (e.g. Days -14 to -1). Change from baseline will be calculated for the Week 22 timepoint.

### 3.3.9. Serum unbound and total ponsegromab concentrations on Day 1 (predose) and Weeks 4, 8, 12, 16, 20, 22, 24 and 32 (Cohorts A, C and D)

*Blood samples will be collected for measurement of serum unbound and total concentrations of ponsegromab as specified in the protocol.*

*In addition, in the Main Cohort (Cohort A)/Cohort C/Cohort D, if the participant consents to the extra sample collection, a flexible PK sample may be collected at 1 week ( $\pm 2$  days) post any dose (ie, collect a sample at Week 1, Week 5, Week 9, Week 13, Week 17, or Week 21 for a dose administered on Day 1, Week 4, Week 8, Week 12, Week 16 or Week 20, respectively).*

Trough concentrations ( $C_{\text{trough}}$ ) are defined as the samples measured pre-dose at Weeks 4, 8, 12, 16, and 20.

### 3.3.10. Serum concentrations of GDF-15 on [REDACTED] (Cohorts A, C and D)

*Blood samples will be collected for measurement of serum concentrations of [REDACTED] GDF-15 at time points specified in the protocol.*

DMB02-GSOP-RF02 7.0 Statistical Analysis Plan Template 31-Jan-2022

PFIZER CONFIDENTIAL

TMF Doc ID: 98.03

Page 25 of 85

*In addition, in the Main Cohort (Cohort A)/Cohort C/Cohort D, if the participant consents to the extra sample collection, a CCI*

Change from baseline and fold change from baseline (i.e. post-dose / baseline), for CCI GDF-15, will be calculated for all post-baseline timepoints.

Additionally, the CCI GDF-15 will be compared to the median healthy volunteer level, at all timepoints, to create an endpoint with two levels ('Yes' and 'No') indicating whether the concentration is below the estimated healthy volunteer median level CCI.

### 3.3.11. Incidence of anti-ponsegromab antibodies, and neutralizing antibodies (Cohorts A, C and D)

*Blood samples will be collected for determination of ADA and NAb as specified in the protocol. Participants found to have anti-ponsegromab antibodies still present at the end of study may be requested to provide additional immunogenicity samples. See Appendix 6 for immunogenicity terms and definitions.*

### 3.3.12. Fold change from baseline in NT-proBNP, hsCRP, albumin and pre-albumin at Week 22 (Cohorts A, C and D)

The fold change from baseline (i.e. post-dose / baseline) in each analyte will be calculated for all post-baseline timepoints. Note: concentrations below the limit of quantification (BLQ) will be set to the lower limit of quantification (LLQ) prior to calculation of the ratio.

### 3.3.13. Fold change from baseline in CCI (Cohorts A, C and D) and CCI (Cohorts C and D only) at Weeks 12 and 22

The fold change from baseline (i.e. post-dose / baseline) in each endpoint will be calculated for all post-baseline timepoints.

Additionally, the % reduction in CCI will be calculated at Weeks 12 and 22, where

$$\% \text{ reduction at Week X} = 100 * (\text{baseline} - \text{Week X}) / \text{baseline}.$$

### 3.3.14. Clinical outcomes (Cohorts A, C and D)

Both investigator-reported and adjudicated events will be recorded.

#### 3.3.14.1. Hierarchical composite endpoint of time to cardiovascular death, number of worsening HF events (hospitalization for HF, or urgent HF visit), time to first worsening HF event and change from baseline in KCCQ-23 CSS at Week 22

The time (days) to cardiovascular death will be calculated for each participant.

The number of hospitalizations for HF and the number of urgent HF visits, over the 22 weeks, will be calculated for each participant. The total number of these worsening heart failure events will also be calculated for each participant, as well as the total number divided by the number of days of study participation (up to Week 22), where 'number of days of study participation' = time from randomization to Week 22, or to time lost-to-follow-up, withdrawal from study, or death. This total will then be multiplied by 154 days in order to provide a 22-week estimate. Similarly, the total number of combined cardiovascular deaths and worsening heart failure events will be calculated.

The composite HF outcome (cardiovascular death, hospitalization for HF or urgent HF visits) will be determined for each participant as well as each individual component as a first event.

The time (days) to first hospitalization for HF and the time (days) to first urgent HF visit will be calculated for each participant. The time to the first of these worsening HF events (hospitalization for HF or urgent HF visit) will also be calculated for each participant.

The change from baseline in KCCQ-23 CSS at Week 22 will be calculated (see Section 3.1.1).

#### **3.3.14.2. Time to first occurrence of the clinical composite of cardiovascular death, hospitalization for HF, or urgent HF visit**

The time (days) to the first occurrence of cardiovascular death or worsening HF events will be calculated.

#### **3.3.14.3. Total number of days alive and out of the hospital over 22 weeks**

The total number of days each participant is alive and out of the hospital (DAOH) over the 22 weeks will be calculated:

- For participants alive, lost to follow-up or withdrawal, at Week 22:
  - 'time on study' = time from randomization to Week 22, or to time lost-to-follow-up or withdrawal
  - 'hospitalization time' = sum of all the durations in hospital during the participant's 'time on study'
  - DAOH = 'time on study' – 'hospitalization time'
- For participants who die before Week 22:
  - 'time on study' = time from randomization to Week 22 (Day 155)
  - 'hospitalization time' = sum of all the durations in hospital during the participant's 'time on study'
  - DAOH = 'time on study' – 'hospitalization time' – number of days from the date of death to Week 22

Additionally, the number of days alive and out of the hospital divided by the number of days of study participation (%DAOH) will be calculated:

$$\% \text{ DAOH} = 100 * (\text{DAOH} / \text{'time on study'}).$$

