
 To compare the effect of ponsegromab versus placebo on clinical outcomes of cardiovascular death, hospitalization for HF, or urgent HF visit and on days alive and out of the hospital in participants with HF. 	
 Hierarchical composite endpoint: 
 Time to cardiovascular death; Number of worsening HF events (hospitalization for HF, or urgent HF visit); Time to first worsening HF event (hospitalization for HF, or urgent heart visit); Change from baseline in KCCQ-23 CSS at Week 22. Time to first occurrence of the clinical composite of cardiovascular death, hospitalization for HF, or urgent heart visit. Total number of days alive and out of the hospital over 22 weeks. Total number of hospitalizations for HF and urgent HF visits over 22 weeks. 	
 Not applicable.

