**6.3.14.4. Total number of hospitalizations for HF and urgent HF visits over 22 weeks**

The number of hospitalizations for HF and urgent HF visits over 22 weeks, as well as the combined total of these worsening HF events, and the total number of combined cardiovascular deaths and worsening HF events, and the total numbers divided by the

number of days of study participation, will be summarized descriptively by treatment group, as described in Section 5.2.1.

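### Event rates scaled per participant let very short follow-up dominate the arm mean, and raw days alive and out of hospital give unobserved days no credit (descriptive tertiary tables only)

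*SAP*

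**What the plan says.** Protocol 3.1 lists two relevant tertiary endpoints: "Total number of days alive and out of the hospital over 22 weeks", and the number of HF hospitalizations and urgent HF visits over the same period.

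**Event totals.** SAP 3.3.14.1 adds up each participant's worsening HF events and divides by that participant's own participation time, defined as "time from randomization to Week 22, or to time lost-to-follow-up, withdrawal from study, or death". It then scales the result: "This total will then be multiplied by 154 days in order to provide a 22-week estimate". A combined total that also counts CV deaths is to be derived in a similar way. SAP 6.3.14.4 reports the plain counts and the totals divided by the "number of days of study participation, will be summarized descriptively by treatment group, as described in Section 5.2.1". Section 5.2.1 specifies the arithmetic mean and SD, median, quartiles and range.

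**DAOH.** SAP 3.3.14.3 has two rules. For participants who are alive, lost or withdrawn, time on study is "time from randomization to Week 22, or to time lost-to-follow-up or withdrawal", and DAOH is that time minus hospital time. For participants who die, time on study is fixed at the full period to Day 155; hospital time and the "number of days from the date of death to Week 22" are both subtracted. It continues: "Additionally, the number of days alive and out of the hospital divided by the number of days of study participation (%DAOH) will be calculated". SAP 6.3.14.3 summarizes both versions by arm. For a death, participation time therefore ends at death in the event rate but runs to Week 22 in %DAOH.

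**The concern.** Both endpoints are meant to describe a fixed 22-week period, but both derivations depend on when a participant leaves. A mean of individual rates gives someone followed for a few days the same weight as a completer, and the short follow-up is what inflates that person's rate. A CV death enters the combined total as an event and also stops the clock that the event is divided by. Raw DAOH scores unobserved days in the same way as days dead.

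What is at stake is the reading of the tables. A few very early deaths or exits, or a difference in withdrawal between arms, could look like a difference in event burden or in time out of hospital.

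**Working it through.** **The plan's constant.** 22 x 7 = 154, and Day 155 - Day 1 = 154. The scaling factor is reproduced. The documents give no expected event rate and no rate of study exit, so those inputs below are assumptions.

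**Event rate, one case.** A CV death after d days with no other event scores 154/d in the combined total; for d = 7 this is 154/7 = 22. Take n = 190 (the 300 mg or placebo arm of Cohort A) and assume 20 participants with one event each.
- All followed for 154 days: mean = 20/190 = 0.105.
- One of the 20 events is a CV death after 7 days: mean = (19 + 22)/190 = 0.216.
- Person-time rate in that second case: 20 x 154/(189 x 154 + 7) = 0.106.

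**Event rate, range.** If the other n - 1 participants average r events per 22 weeks, the arm mean is ((n - 1)r + 154/d)/n, and the pooled rate is ((n - 1)r + 1)/((n - 1) x 154 + d) x 154. With n = 190 and d = 7:

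| Assumed r | Mean of individual rates | Multiple of r | Pooled rate |
|---|---|---|---|
| 0.05 | 0.166 | 3.31 | 0.0553 |
| 0.10 | 0.215 | 2.15 | 0.1053 |
| 0.20 | 0.315 | 1.57 | 0.2052 |
| 0.30 | 0.414 | 1.38 | 0.3052 |

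The mean at least doubles when d <= 154/((n + 1)r). For n = 190:
- r = 0.05: 154/(191 x 0.05) = 16.1, so by about Day 16.
- r = 0.10: 154/(191 x 0.10) = 8.1, so by about Day 8.
- r = 0.30: 154/(191 x 0.30) = 2.7, so by about Day 2.

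The HF-only rate inflates in this way only if an HF event comes before the early exit or death. A death with no HF event adds zero to it.

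**DAOH.** Let t be the days from randomization to exit or death, and h the hospital days.
- Withdrawn alive: DAOH = t - h.
- Died: DAOH = 154 - h - (154 - t) = t - h.

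The two are identical. With t = 40 and h = 0, both score 40. %DAOH is 100 x 40/40 = 100% for the withdrawal and 100 x 40/154 = 26% for the death.

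**Size for DAOH.** Assume no deaths or admissions, and exits at the midpoint (77 days lost per exit). The difference in mean raw DAOH between arms is then the exit imbalance x 77:
- 1 point: 0.01 x 77 = 0.8 days.
- 3 points: 0.03 x 77 = 2.3 days.
- 5 points (for example 8% v 3%): 0.05 x 77 = 3.9 days.

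For comparison, a true 2-point difference in mortality at the midpoint gives 0.02 x 77 = 1.5 days. With no deaths or admissions, the arm-level ratio of summed DAOH to summed time on study, x 154, is 154 in both arms whatever the imbalance.

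**The case against.** The strongest reply is that little rests on these tables, and most of it stands.

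- A reader might infer that the plan cannot tell withdrawal from death. It can: %DAOH is reported beside raw DAOH and separates them, and SAP 6.5.2 tabulates withdrawal, loss to follow-up and death by arm. What remains is that %DAOH gives an early withdrawal with no admission the maximum score, with the same weight as a completer.
- A reader might infer that any early death doubles the event rate. It does not. The death must be cardiovascular, it affects the combined total, and in an arm of 190 it must come within roughly the first 2 to 16 days at the assumed rates. Plain counts, medians and ranges are also shown, so a value of 22 would be visible as the maximum.
- A reader might infer that the trial could reach a false conclusion. SAP 6.3.14.3 and 6.3.14.4 are descriptive, and SAP 5.1 plans no formal testing for such endpoints. The win ratio, logistic and Cox analyses in SAP 6.3.14.1 and 6.3.14.2 do not use these formulas.
- The 15% in Protocol 9.5 is a discontinuation rate with no arm difference stated. Protocol 7.1 and 7.2.1 keep participants who stop study drug in follow-up, so study exits may be fewer. The withdrawal imbalances above are illustrations.
- For the combined total, the x 154 step rests on the word similarly in SAP 3.3.14.1. This does not matter for the relative inflation, because a constant factor cancels.

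None of this makes the mean of individual rates a good summary of event burden.

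**Conclusion.** The formulas behave as described. The mean of scaled individual rates is dominated by very short follow-up: one CV death after 7 days moves the combined rate in a 190-person arm from 0.105 to 0.216, against a person-time rate of 0.106, if 20 participants have one event each. Doubling needs a CV death by about Day 16, 8 or 2 at assumed rates of 0.05, 0.10 or 0.30. Raw DAOH is t - h for both withdrawal alive and death; that result is exact and needs no assumption. The size of any resulting difference between arms depends on exit patterns that the documents do not give. Severity is minor: these are descriptive tertiary summaries, and no test, model, or primary or secondary conclusion changes.

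**What to change.** 1. In SAP 3.3.14.1 and 6.3.14.4, replace the summary of per-participant scaled rates with an arm-level rate: total events / total participant-days x 154. Give a 90% CI that allows for repeated events within a participant, for example a bootstrap that resamples participants. Keep the unscaled counts.
2. In SAP 3.3.14.3 and 6.3.14.3, keep raw DAOH for all participants, with a footnote that days after withdrawal or loss to follow-up are not counted. Add the arm-level ratio, sum of DAOH / sum of time on study x 154, and show the number of early exits alive in each arm. Because deaths carry 154 days and withdrawals carry fewer, the ratio can still vary with withdrawal when there are deaths, though less than raw DAOH; the exit counts let the reader judge this.
3. Do not restrict raw DAOH to participants whose status is known through Week 22. That would keep every death and drop every withdrawal.

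The cost is SAP wording and minor table programming. No new data are needed and the design does not change.

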**3.3.14.4. Total number of hospitalizations for HF and urgent HF visits over 22 weeks**

See Section 3.3.14.1.

**3.3.15. Serum unbound and total ponsegromab PK parameters (Cohort B only)**

*Blood samples will be collected for measurement of serum unbound and total concentrations of ponsegromab as specified in the protocol.*

The following PK parameters for unbound and total ponsegromab after 1st dose on Day 1 and 4th dose on Day 85, will be derived, using the PK concentration analysis set for the open-label, PK cohort, from the concentration-time profiles using noncompartment methods, as data permit.

**Table 2. Derivation of Ponsegromab PK Parameters**

Parameter	Day(s)	Definition	Method of Determination
AUC tau	1, 85	Area under the plasma concentration-time profile from time zero to time tau, the dosing interval, where tau = 28 days for Q4W dosing.	Linear/Log trapezoidal method
C max	1, 85	Maximum plasma concentration during the dosing interval	Observed directly from data
T max	1, 85	Time for C max	Observed directly from data as time of first occurrence
AUC tau (dn)	1, 85	Dose normalized AUC tau	AUC tau /Dose
C max (dn)	1, 85	Dose normalized C max	C max /Dose
C min	1, 85	Minimum plasma concentration during the dosing interval	Observed directly from data
CL/F	85	Apparent clearance for oral dosing	Dose/AUC tau
R ac	85	Observed accumulation ratio	Day 85 AUC tau /Day 1 AUC tau
R ac , C max	85	Observed accumulation ratio for C max	Day 85 C max /Day 1 C max
PTR	85	Peak-to-trough ratio	C max /C min
t 1/2 *	85	Terminal half-life	Loge(2)/kel, where kel is the terminal phase elimination rate constant calculated by a linear regression of the log-linear concentration-time curve
V z /F*	85	Apparent volume of distribution for oral dosing	Dose/(AUC tau * kel)

\*As data permits.

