2.2.2.2. Summary of Pharmacokinetics

Following single dose administration of ponsegromab to healthy non-Japanese participants, SC absorption of unbound ponsegromab for the 3 to 300 mg dose groups occurred with median T_{max} ranging from 2.25 to 7.00 days. In general, over the 10 to 300 mg dose range, increases in geometric mean unbound C_{max} in serum were approximately dose-proportional and increases in unbound AUC_{last} and AUC_{inf} in serum appeared to be greater than dose-proportional. The geometric mean CL/F appeared to decrease with increasing dose, and mean terminal $t_{1/2}$ increased with increasing dose, ranging from 3.52 to 11.1 days across the 10 to 300 mg dose groups.

Following single doses of SC ponsegromab in healthy participants, absorption of total ponsegromab occurred with median T_{max} ranging from 6.00 to 14.0 days across the 1 to 300 mg dose groups. In general, increases in geometric mean total C_{max} , AUC_{last} , and AUC_{inf} in serum appeared to be less than dose-proportional over the 10 to 100 mg dose range, while increases in exposure from 100 to 300 mg doses were largely dose proportional. The mean terminal $t_{1/2}$ values increased from 20.1 days for the 10 mg group to 30.9 days for the 300 mg group. The long terminal $t_{1/2}$ of total ponsegromab in serum is driven primarily by the half-life of bound ponsegromab (ponsegromab-GDF-15 complex), as the terminal $t_{1/2}$ of unbound ponsegromab observed over the same dose range was much shorter. Unbound ponsegromab (not total ponsegromab) is the active moiety that accounts for pharmacological activity of the drug.

CCI [REDACTED]

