3.2. Open-Label, PK Cohort (Cohort B)

Objectives	Endpoints	Estimands
Secondary:	Secondary:	Secondary:

 To evaluate the safety and tolerability of ponsegromab in participants with HF and elevated circulating GDF-15 concentrations. 	
 Incidence of TEAEs, TSEAEs, abnormal laboratory results, and vital signs. 	
 There are no defined estimands for the incidence of TEAEs, TSEAEs, abnormal laboratory results, and vital signs, and these endpoints will be analyzed using Pfizer data standards as applicable.
Tertiary/Exploratory:	Tertiary/Exploratory:	Tertiary/Exploratory:

 To evaluate the PK of ponsegromab following repeated SC administration in participants with HF and elevated circulating GDF-15 concentrations. 	
 Serum unbound and total ponsegromab PK parameters after 1st dose on Day 1 and 4th dose on Day 85: AUC_{tau}, C_{max}, T_{max} and as data permit, t_{1/2}, CL/F, Vz/F, PTR after 4th dose. 	
 There are no defined estimands for PK endpoints.

 To characterize the effect of ponsegromab on circulating GDF-15 concentrations in participants 	Serum concentrations of GDF-15 on Day 1 and Weeks 1, 2, 3, 4, 8, 12, 13, 14, 15, 16 and 18.	
 Not applicable

Objectives	Endpoints	Estimands
with HF and elevated circulating GDF-15 concentrations.		

 To characterize the immunogenicity of ponsegromab in participants with HF and elevated circulating GDF-15 concentrations. 	
 Incidence of ADA, and NAb. 	
 Not applicable.

 To evaluate the effect of ponsegromab on NT-proBNP in participants with HF and elevated circulating GDF-15 concentrations. 	
 Fold change from baseline in NT-proBNP at Weeks 12 and 16. 	
 Not applicable.

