8.5. Pharmacokinetics

Blood samples of approximately 4 mL, to provide a minimum of 1.5 mL serum, will be collected for measurement of serum unbound and total concentrations of ponsegromab as specified in the respective [SoA](#) (ie, [Table 1](#) for the Main Cohort (Cohort A)/Cohort C/Cohort D and [Table 2](#) for the open-label, PK cohort).

In addition, in the Main Cohort (Cohort A)/Cohort C/Cohort D, if the participant consents to the extra sample collection, a flexible PK sample may be collected at 1 week (± 2 days) post any dose (ie, collect a sample at Week 1, Week 5, Week 9, Week 13, Week 17, or Week 21 for a dose administered on Day 1, Week 4, Week 8, Week 12, Week 16 or Week 20, respectively), in conjunction with the flexible PD sample collection (see [Section 8.7.1](#)). It will not be considered a protocol deviation if the participant chooses not to have this additional visit.

Instructions for the collection and handling of biological samples will be provided in the laboratory manual or by the sponsor. The actual date and time (24-hour clock time) of each sample will be recorded. In some instances, as specified in the respective [SoAs](#), the samples from the participant may be collected at their home or current residence.

The actual times may change, but the number of samples will remain the same. Collection of samples within the protocol-allowed visit window, as defined in [SoA](#) or noted above will not be captured as a protocol deviation, as long as the exact time of the collection is noted on the source document and the CRF.

Samples will be used to evaluate the PK of ponsegromab. Samples collected for analyses of ponsegromab serum concentrations may also be used to evaluate safety or efficacy aspects related to concerns arising during or after the study, for metabolite identification and/or evaluation of the bioanalytical method, or for other internal exploratory purposes.

Genetic analyses will not be performed on these serum samples unless consent for this was included in the informed consent. Participant confidentiality will be maintained.

Samples collected for measurement of serum concentrations of ponsegromab (unbound and total) will be analyzed using a validated analytical method(s) in compliance with applicable SOPs.

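### No PK sample is scheduled in the first days after a dose, so the unbound Tmax, Cmax, AUCtau and CL/F that SAP Table 2 derives for Cohort B are limited or biased by the weekly schedule

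*SAP*

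**What the plan says.** Protocol 3.2 lists as a tertiary/exploratory endpoint for Cohort B "Serum unbound and total ponsegromab PK parameters after 1st dose on Day 1 and 4th dose on Day 85". SAP 3.3.15 says these are derived by non-compartmental methods. In SAP Table 2, Tmax is "Observed directly from data as time of first occurrence", Cmax is also read from the observed values, AUCtau uses the linear/log trapezoidal rule over 28 days, and CL/F is Dose/AUCtau on Day 85.

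The Cohort B schedule (Protocol 1.3, Table 2) has PK samples at Weeks 0, 1, 2, 3, 4, 8, 12, 13, 14, 15, 16 and 18, and at early termination. Samples on dosing days are taken before the dose. In Cohorts A, C and D dosing-day samples are also pre-dose. Protocol 8.5 adds that "a flexible PK sample may be collected at 1 week", with a window of ±2 days; this visit is optional.

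Protocol 2.2.2.2 reports, for single doses in healthy participants, that "SC absorption of unbound ponsegromab for the 3 to 300 mg dose groups occurred with median T_{max} ranging from 2.25 to 7.00 days". For total drug it reports "median T_{max} ranging from 6.00 to 14.0 days across the 1 to 300 mg dose groups". The unbound half-life rises with dose, "ranging from 3.52 to 11.1 days across the 10 to 300 mg dose groups". The same section states: "Unbound ponsegromab (not total ponsegromab) is the active moiety that accounts for pharmacological activity of the drug".

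**The concern.** A peak that comes before the first sample cannot be observed. If unbound drug peaks at 2 to 5 days and the first sample is at about day 7, the recorded Tmax is the visit day and the recorded Cmax is a point on the falling limb. The trapezoid from the pre-dose sample to day 7 is a straight line under the peak, so AUCtau is too small and Dose/AUCtau too large.

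The stated purpose of Cohort B (Protocol 4.1) is a fuller account of PK and of the PK/PD relationship in heart failure, and unbound drug is the active moiety. The parameters most exposed are those of the analyte that matters most there. Nothing in either document mentions the limitation. A population PK/PD analysis, which might deal with it, is optional (SAP 6.5.4).

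A smaller point sits in the same table. Cmin is the minimum over the dosing interval and is listed for Day 1. On Day 1 the interval opens with the pre-dose sample. Prior exposure to ponsegromab is an exclusion, so this sample should be below quantification, and SAP 5.3.1 sets such PK values to zero. SAP Table 3 then asks for a geometric mean of Cmin, which zeros do not allow.

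**Working it through.** The plan states no figure of its own on this point, so there is nothing to reproduce.

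**Step 1: days from dose to first post-dose sample** (visit days and windows from the two schedules in Protocol 1.3)

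- Cohort B, dose 1: Day 8 ±2 after Day 1. Nominal 8 − 1 = 7 days, range 5 to 9.
- Cohort B, dose 4: Day 92 ±1 after Day 85 ±2. Nominal 92 − 85 = 7 days. If windows stack, the range is 91 − 87 = 4 to 93 − 83 = 10 days.
- Flexible visit, Cohorts A, C and D: 1 week ±2 days, so 5 to 9 days.

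**Step 2: model (an assumption)**

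Linear, one compartment, first-order absorption: f(t) = ka/(ka − ke) × (e^(−ke·t) − e^(−ka·t)), in units of F·Dose/V, with ke = ln 2 / half-life. ka is solved from Tmax = ln(ka/ke)/(ka − ke), where Tmax is the single-dose value. Four doses 28 days apart are superposed. Samples at 0, 7, 14, 21 and 28 days are compared with the full curve.

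**Step 3: worked case, half-life 11.1 days, Tmax 4 days**

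ke = 0.693/11.1 = 0.0624 and ka = 0.647. Check: ln(0.647/0.0624)/(0.647 − 0.0624) = 4.0.

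Dose-4 values at 0, 7, 14, 21 and 28 days: 0.232, 0.853, 0.558, 0.361, 0.233.

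- 0-7 (linear, rising): 7 × (0.232 + 0.853)/2 = 3.80
- 7-14 (log): 7 × (0.853 − 0.558)/ln(0.853/0.558) = 4.87
- 14-21 (log): 3.17
- 21-28 (log): 2.05

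The sampled AUCtau is about 13.88 and the true value 16.00, a ratio of 0.867. CL/F is overstated by 16.00/13.88 − 1 = 15%. Sampled Cmax is 0.853 against a true 0.962, a ratio of 0.887. The later segments are close to exact; nearly all the loss is in the first week.

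**Step 4: results for dose 4, first sample at 7 days**

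| Half-life | True Tmax | Observed Tmax | Cmax | AUCtau | CL/F |
|---|---|---|---|---|---|
| 11.1 d | 2.25 d | 7 d | −23% | −18% | +22% |
| 11.1 d | 4 d | 7 d | −11% | −13% | +15% |
| 11.1 d | 7 d | 7 d | −1% | −7% | +8% |
| 7 d (assumed) | 2.25 d | 7 d | −32% | −27% | +36% |
| 7 d (assumed) | 7 d | 7 d | 0% | −9% | +10% |
| 3.52 d | 2.25 d | 7 d | −49% | −45% | +81% |

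Half-life rises with dose, so 11.1 days is the 300 mg end of the stated range and 3.52 days the 10 mg end, which is outside the trial's doses. The 7-day row stands in for a lower trial dose; the documents give no figure for one.

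If the first sample after dose 4 falls anywhere from 4 to 10 days (half-life 11.1 days), AUCtau is 5% to 26% low and CL/F 6% to 36% high. After dose 1, with the first sample at 7 days and the same half-life, AUCtau is about 10% to 22% low.

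**Step 5: total drug.** With the stated 30.9-day half-life at 300 mg and Tmax of 6 to 14 days, the same calculation gives dose-4 Cmax at 0.98 to 1.00 of true and AUCtau at 0.95 to 0.98.

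**The case against.** The strongest reply is that the Tmax range is not for the trial's doses. It spans 3 to 300 mg in healthy participants and is not broken down by dose, while the trial uses 100, 200 and 300 mg in heart failure. If true unbound Tmax is near 7 days, the Cmax bias all but disappears and the AUCtau bias falls to about 7% to 9%. This stands, and it is why the result is given as a range. The linear model is also a simplification: Protocol 2.2.2.2 reports unbound AUC rising more than in proportion to dose and CL/F falling with dose. The percentages are illustrative. The direction for AUCtau and CL/F was the same in every case run.

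A reader might infer more than the documents support:

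- *That no sample can fall within 5 days of a dose.* Stacked windows allow one 4 days after dose 4, and early-termination samples have no fixed day. The point concerns what is scheduled.
- *That all the Cohort B parameters are unreliable.* Total-drug Tmax lies within the weekly sampling and its parameters are nearly intact. The unbound AUC accumulation ratio is also little affected, because most of the bias cancels: at 11.1 days the overstatement is about 3% to 5%.
- *That a planned comparison with healthy volunteers is spoiled.* SAP 6.3.15 plans only descriptive summaries and dose-normalised plots.
- *That the trial's conclusions are at risk.* These are exploratory endpoints in about 20 participants, with no hypothesis test. The primary and secondary efficacy analyses do not use them.

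Protocol 8.5 lets sampling times be changed or added without an amendment. That makes a remedy easier; it does not supply one.

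**Conclusion.** The point holds in this limited form. At nominal times observed unbound Tmax is 7 days for any true value up to 7 days, so it carries little information. At an 11.1-day half-life, dose-4 unbound AUCtau is about 7% to 18% low and CL/F about 8% to 22% high. Cmax is 1% to 23% low, and near zero bias is possible if the true peak is at about 7 days. Shorter half-lives make it worse. The sizes rest on the assumed linear model and on the healthy-participant Tmax range carrying over to 100-300 mg in heart failure. The schedule facts and the direction of the AUCtau and CL/F bias do not depend on the exact inputs. The effect is confined to unbound drug and to exploratory endpoints, but it bears on the purpose for which Cohort B was added. The Day 1 Cmin definition is a separate, minor wording fault.

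**What to change.** (a) **Flexible visit, Cohorts A, C and D.** For participants not yet sampled, widen the optional PK/PD visit from 1 week ±2 days to 2-9 days after a dose, with the day spread across participants. No samples are added. The cost is fewer samples at exactly 1 week. The SAP's first interim analysis had a data cutoff of 08 October 2024, so much of Cohort A may already be past this visit; the gain would come mainly from Cohorts C and D. This gives early unbound concentrations in heart failure but does not repair the Cohort B parameters.

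(b) **SAP 3.3.15 and 6.3.15.** State that unbound Tmax and Cmax in Cohort B are limited by the first weekly sample, that unbound AUCtau is biased low and CL/F high, and that none of them is to be read as an estimate of the true value. This is wording only.

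(c) **SAP Table 2, Cmin on Day 1.** Define it as the post-dose minimum or the Week 4 pre-dose sample, or drop it. This is wording only.

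Two larger remedies are not asked for. An extra Cohort B draw at about day 3 would bring dose-4 AUCtau to 0.92-0.98 of true in this model (half-lives 7 and 11.1 days), but it needs added visits. Taking unbound Cmax and Tmax from the population model would rest on an optional analysis with no scheduled early unbound samples in heart failure.
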